 Collection of skin bacteria by the tape-stripping method is based on the method described in previous studies [6]. Two D-squame standard sampling discs (Monaderm, Monaco, France) will be applied consecutively to the skin area (one tape on the left malar cheek, one tape on the right malar cheek), using a new piece for each application, for 1 minute. The tape will be peeled off from skin with sterile forceps. For skin microbiome, the two tapes will be pooled for analysis and stored in a sterile 1.5-mL centrifugation tube at -80°C until ready for analysis.
 - b) Skin biopsies: To define histological changes to collagen, elastin, and cellular senescence, 5-mm skin punch biopsies will be obtained. Subjects (n=30) will be instructed to apply topical HPE (right upper inner arm). At baseline, a 5-mm punch biopsy from the left upper inner arm will be obtained from untreated skin. At week 12, a 5-mm punch biopsy from the right upper inner arm will be obtained from HPE-treated skin. Each subject (n=30) will therefore undergo 2 total skin biopsies. Subject renumeration provided. The first 30 willing subjects will be recruited.

- i) In this study, we will remove a small piece of skin from the left upper inner arm (untreated) at baseline and right upper inner arm at week 12 (treated topical HPE). This is called a skin biopsy.
- ii) The site(s) or area of the skin identified for skin biopsy will be cleaned with antiseptic and may be numbed by injecting a small amount of numbing medicine, through a small needle. Some people (fewer than 1 in 10,000) are allergic to the shot you will get to numb the area where the skin is taken. The biopsy procedure is conducted by taking a larger circular tool or needle (about 1/5th of an inch in diameter), inserting it into the skin and removing the core piece that fits inside the circle. There could be bleeding from the site, and this might require placement of a stitch. Heavy bleeding from a skin biopsy is rare. Other complications could include pain, and there is the possibility of the biopsy site becoming infected. Skin biopsies cause infections about 10% of the time. A small scar will form at the biopsy site. The scar is usually much smaller than the original biopsy. The procedure is conducted using sterile instruments after disinfectant or antiseptic cleaning of the skin.
- 2) Self-assessment [Time Frame: 6, 12, 26- and 52-weeks]
 - a) Global Aesthetic Improvement Scale [7]:

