 - i) 1 Exception: Very much improved and optimal cosmetic result for the subject
 - ii) 2 Moderate: Much improved and marked improvement in condition, but not optimal for subject; touch-up would slightly improve the result
 - iii) 3 Slight: Improved with obvious improvement but touch-up or retreatment indicated
 - iv) 4 No change: Appearance essentially the same as original condition
 - v) 5 Worse: Appearance worse than original condition
 - b) Cosmetic Improvement Scale [8]: The following parameters will be scored as a percentage of total responses from participants.
 - i. Percentage of subjects satisfied or very satisfied with the treatment
 - ii. Percentage of subjects who would recommend the treatment to a friend
 - iii. Percentage of subjects reporting high likelihood of continuing treatment
 - iv. Percentage of subjects reporting treatment positively or negatively affected self-esteem
 - v. Percentage of subjects reporting no, minimal, moderate, or significant improvement in fine lines and wrinkles, skin tone, skin smoothness and/or puffiness

Data collection

Data collection, processing, transmission, and storage will follow Mayo Clinic Data Protection Standards. Redcap, a Mayo-endorsed, password protected HIPAA-compliant system, will be used as the electronic data collection and management system. It allows data tracking and downloads to statistical analysis packages. Participant informed consents will be tracked using Ptrax. Participant questionnaires will be collected using REDCap.

Canfield VISIA CR Gen 5 with 3DPrimos will be used to evaluate qualitatively and quantitatively skin profile changes. If Canfield is processing any data on behalf of Sponsor, Canfield shall do so in strict accordance and compliance with applicable laws, rules, and regulations, including to the extent applicable, the Health Insurance Portability and Accountability Act of 1996 and the Regulation (EU) 2016/679 of the European Parliament and the Council of 27 April 2016 on the protection of natural persons with regard to the processing of personal data and on the free movement of such data (GDPR), and with Sponsor's instructions, and it shall not utilize said data for any other purpose whatsoever without obtaining data subject's consent first.

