Informed consent must be obtained with signing of the ICF prior to performing any study-related procedure.

Assessments during the screening visit will include:

- Demographic data
- Medical and surgical history
- Medication history
- Concomitant medication
- Concomitant procedures
- Physical examination

Based on the result of the screening visit and review of the eligibility criteria, the PI will assess each potential subject's eligibility for study inclusion. If the subject is found eligible, she can then be enrolled. The screening visit results will be recorded in the subject's electronic case report form (e-CRF) and the subject will be scheduled for a subsequent visit to complete additional baseline assessments,

Enrolled subjects will then initiate baseline visit (V0) at the same time during which they will complete their baseline assessments and initiate their treatment.

General assessment

- Baseline VISIA-CR imaging
- Photography
- Skin microbiome facial swab and tape-stripping (n=80 skin swab and tape-stripping)
- Skin biopsy (n=30)
 - o Left upper inner arm (untreated skin)

Treatment

- Treatment: Topical HPE twice daily for study duration.
- Study staff will demonstrate treatment application.
- Subject instructions and treatment log will be provided.
- Each subject will receive the first cosmetic kit, which will include gentle cleanser, unscented bar soap, HPETM product, SkinceuticalsTM CE Ferulic serum, sunscreen and moisturizer. A second cosmetic kit will be provided at week 6 visit.

• For questions, subjects will be provided contact email: [contact]

Visit 1: Follow-up at 6-weeks

- VISIA-CR imaging
- Photography
- Topical treatment jars will be weighed to ensure correct application amount.
- Subject treatment log will be reviewed.

Specific assessment (cosmetic evaluation questionnaires)

- Global Aesthetic Improvement Scale
- Cosmetic Improvement Scale

Treatment assessment

- Continuation of Topical HPE twice daily as indicated.
- Study staff will re-demonstrate treatment application.
- Each subject will receive their second cosmetic kit, which will include gentle cleanser, unscented bar soap, HPETM product, SkinceuticalsTM CE Ferulic serum, sunscreen and moisturizer.
- For questions, subjects will be provided contact email: [contact]

Visit 2: Follow-up at 12-weeks

- VISIA-CR imaging
- Photography
- Skin microbiome facial swab and tape-stripping (n=80 skin swab and tape-stripping)
- Skin biopsy (n=30)
 - Right upper inner arm (HPE)

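### Two GAIS grades carry labels that conflict with their descriptors, and the plan does not say that subjects see their baseline image when they rate change

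*Combined protocol and SAP*

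**What the plan says.** Under Endpoints, Secondary, item 2(a), the combined protocol and SAP lists the five self-rated grades:

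- "1 Exception: Very much improved and optimal cosmetic result for the subject"
- "2 Moderate: Much improved and marked improvement in condition, but not optimal for subject", followed by a clause on touch-up
- "3 Slight: Improved with obvious improvement but touch-up or retreatment indicated"
- "4 No change: Appearance essentially the same as original condition"
- "5 Worse: Appearance worse than original condition"

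The self-assessment time frame is 6, 12, 26 and 52 weeks. Weeks 26 and 52 are for main-study subjects who choose to continue (Study Design and Methods; footnote to Table 1). The 2X substudy of 50 schedules its surveys at baseline, 6 and 12 weeks only.

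The Visit 0 list includes "Baseline VISIA-CR imaging" and photography. Table 1 repeats both at every later visit. No section says whether the subject looks at the baseline image while completing the GAIS.

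Study procedures has all 80 main-study subjects apply HPE to the whole face and decolletage; the comparator goes on the left dorsal hand only. The Data Analysis Plan reports categorical data as counts and percentages, and sets no GAIS responder cut-off.

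**The concern.** A change scale needs two things: a fixed reference to judge against, and grades that mean the same to every respondent. Here the reference is the subject's own skin weeks or months earlier, and the plan does not say how it is put before the subject. Two of the three improvement grades say one thing in the label and something stronger in the descriptor. Someone with a slight change has to decide which half of the line to believe, and a reader of the report cannot tell which half was used. A *Slight* answer could fairly be tabulated as slight improvement or as obvious improvement.

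The touch-up and retreatment clauses add to this. Part of what separates grades 1, 2 and 3 is whether further treatment is needed, and a subject who applies the product twice daily throughout has no such decision to report.

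At stake is the interpretation of a secondary endpoint. With no untreated or comparator-treated face, errors of recall, expectation or reading do not cancel in a between-group contrast. They go straight into the reported percentages.

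**Working it through.** **1. Label against descriptor.**

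| Grade | Label | Strength of descriptor | Agreement |
|---|---|---|---|
| 1 | Exception | very much improved, optimal | same direction; label looks like a slip for exceptional |
| 2 | Moderate | much improved, marked | conflict: descriptor stronger |
| 3 | Slight | obvious | conflict: descriptor stronger |
| 4 | No change | essentially unchanged | agree |
| 5 | Worse | worse | agree |

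Two of five grades conflict. The Cosmetic Improvement Scale, item 2(b), completed at the same visits, has a *minimal* level between none and moderate. Read by descriptor, the GAIS has no counterpart to it.

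**2. Where a small, non-obvious improvement goes.** By label it is grade 3. By descriptor it falls short of grade 3 and, strictly, is not grade 4 either; grade 4 is the nearest. Let q be the share of subjects with obvious or greater improvement, s the share with a small one, and f the fraction of that small group who go by the label. If the rest choose grade 4, then

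share in grades 1 to 3 = q + s × f.

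As f runs from 0 to 1 the share moves by s, so the effect of reading is at most s. The documents give neither s nor f. Assuming s = 10% to 20% of 80 subjects: 0.10 × 80 = 8 and 0.20 × 80 = 16 people, or at most 10 to 20 points. This bound simply returns the assumed s, and reaches it only if everyone in the group reads the item the same way.

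For scale, the 95% Wilson half-width at 50% with n = 80 is

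1.96 × √(0.25/80 + 1.96²/(4 × 80²)) / (1 + 1.96²/80) = 10.7 points.

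The direction is not fixed. If a small change should count as improvement, descriptor readers understate it. If only an obvious change should count, label readers overstate it.

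**3. Recall and response error.** There is no stated response rate or error rate to reproduce. Let p be the true improved share and m the fraction of unimproved subjects who rate themselves improved. Then observed share = p + (1 − p) × m. With assumed m from 10% to 30%:

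- p = 30%: 0.30 + 0.70 × 0.10 = 37%, up to 0.30 + 0.70 × 0.30 = 51%
- p = 50%: 55% to 65%
- p = 70%: 73% to 79%

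This model can only push upwards. Error the other way, with a fraction d of improved subjects reporting no change, gives p × (1 − d): for p = 50% and d from 10% to 30%, 45% down to 35%. These figures show what is possible; they estimate nothing.

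**4. The baseline reference.** Grades 4 and 5 name the baseline condition; grades 1 to 3 imply it through the word improved. A Visit 0 image and a current image should both be on file at every GAIS visit. The plan neither requires nor rules out showing them. The longest scheduled interval from baseline is 12 weeks for the substudy and for main-study subjects who stop there, and 52 weeks for those who opt in.

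**The case against.** The strongest reply is that this is a small matter of wording on a minor endpoint. The GAIS is one of two secondary self-assessments. Image-based change in photoaging scores, which does not depend on the subject's memory, is listed under the primary endpoints. The Cosmetic Improvement Scale already gives a subject with a small change somewhere to record it. With no responder cut-off set, all five grades can be tabulated and the boundary between grades 3 and 4 need not drive a headline figure. The scale is attributed to a cited source, and the REDCap form is not in the documents, so subjects may see only the labels or only the descriptors. All of this limits the consequence. None of it reconciles the two conflicting lines or says how the baseline is presented.

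A reader might infer that subjects rate from memory. The documents do not say so; they are silent, and staff may well show the photographs. A reader might also infer that the wording inflates improvement. It need not: the descriptor of grade 3 sets a higher bar than its label, so it could equally deflate the result. Three of the five grades being improvements makes overstatement plausible in an open-label setting, but is not evidence of it.

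**Conclusion.** The point holds as a cheap improvement. Grades 2 and 3 have labels weaker than their descriptors, the touch-up and retreatment clauses do not fit twice-daily topical use, and no procedure puts the baseline image in front of the subject. With no concurrent control on the face, the GAIS result is open to recall and response bias of unknown size; the label conflict by itself has no fixed direction. The 8 to 16 subjects in the working rest wholly on an assumed share with a small improvement and on treating grades 1 to 3 as improved, which the plan does not do.

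It would go too far to call the self-rated result unreliable or overstated, or to present a 52-week recall interval as general: weeks 26 and 52 are optional, and the substudy's surveys stop at week 12. No sample-size figure and no image-based endpoint is affected.

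**What to change.** At each GAIS rating, show the subject the standardised Visit 0 image beside the current one, and write that step into the visit procedures. On the REDCap form, give each grade one consistent wording so that label and descriptor agree, and leave out the touch-up and retreatment clauses. Report counts and percentages for all five grades, using the words the subjects actually saw. If ratings have already been collected on the present wording, report those separately from ratings on the revised form.

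The cost is about a minute per visit, since the images are already scheduled, plus one form edit and some loss of comparability with the cited scale. The change makes the rating less dependent on recall and gives each grade one meaning. It does not supply a control for the face or remove the expectation that comes with knowing the treatment, so the GAIS should still be described as an uncontrolled self-rating.

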Subjects will undergo clinical evaluations as outlined below on day 0, week 6 and week 12, which will include a subject questionnaire rating subjective parameters (Global Aesthetic Improvement Scale and Cosmetic Improvement Scale) and high resolution, standardized imaging (Canfield VISIA CR Gen 5 with 3DPrimos) to evaluate targeted fluorescence imaging of protoporphyrin-IX and coproporphyrin-III for measuring microbial activity, standard white light and polarized imaging for textural and topographical information, RBX® Red/Brown processing for measuring pigmentation, and 3D imaging with Primos for roughness and volumetric measurements. All subjects will have skin microbiome analysis performed from the face at baseline and week 12 unless they did not meet criteria (i.e., washed face 3-hours prior to clinical visit, which would shift the skin microbiome; or prior allergy to adhesives) or unless they decline. Skin microbiome analysis would be performed by skin swab and tape-stripping. Subjects (up to n=80) who are interested in being involved for a longer duration in the study will be followed to 26-week and 52-week time points for long-term analysis of topical HPE on facial and decolletage skin per subject preference. Subject renumeration will be provided for skin biopsies, and follow-up 26- and 52-week visits.

At the end of the study participants will be asked if they would like to participate in a video interview using an interview guide. Participants that don't continue use of the products after 12 weeks, will be given the option to return to the clinic for photos at 6 months and 12 months. These participants will be given another bottle of the study product.

We will use a zoom type platform and capture study participants thoughts and attitudes towards overall skincare routines and HPE (plated) TM SkinScience product. Each selected patient will be recorded in a 30-minute interview. The interviews will be transcribed, edited for patient testimonials (2–3-minute videos) and used in marketing and patient education materials.

Amendment 2X concentration study:

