 The study involves data that exist at the time of IRB submission and data that will be generated after IRB submission. Include this activity in the Methods section. Examples The study plans to conduct a retrospective chart review and ask subjects to complete a questionnaire. The study plans to include subjects previously diagnosed with a specific disease and add newly diagnosed subjects in the future. 					
The study will use data that have been collected under another IRB protocol. Include in the Methods section and enter the IRB number from which the research material will be obtained. When appropriate, note when subjects have provided consent for future use of their data and/or specimens as described in this protocol.					
Enter one IRB number per line, add more lines as needed					
Data Specimens Data & Specimens					
☐ Data ☐ Specimens ☐ Data & Specimens					
☐ Data ☐ Specimens ☐ Data & Specimens					
Data Analysis					

Power analyses may not be appropriate if this is a feasibility or pilot study, but end-point analysis plans are always appropriate even if only exploratory. Provide all information requested below, or provide justification if not including all of the information.

Data Analysis Plan:

All continuous data will be analyzed using independent 2-group t tests and reported as means \pm standard deviations. Categorical data will be compared between the 2 groups using chi-square tests and reported as counts and percentages. Nonparametric equivalents Wilcoxon rank-sum and Fisher exact tests will be used as needed for nonnormal distributions and low variable numbers, respectively. Treatment effects on outcomes will be compared between baseline versus HPE and HPE versus market competitor group with a significance level of p < 0.05.

Endpoints

Primary:

Evaluation of the tolerability of the study product.

- a. Nature, incidence, and severity of adverse events (AEs)
 - 1) Defined as any untoward or undesirable medical occurrence in the form of signs, symptoms, abnormal findings, or diseases that emerge or worsen relative to baseline (i.e., if present upon study entry) during the study regardless of causal relationship.
 - 2) Assessment
 - i. Incidence and severity of AEs (mild, moderate, severe)
 - ii. Relationship of AEs to study product (probable, possible, unlikely, unrelated)
 - 1. If possibly or probably related to the study product, determine whether related to the product itself or procedures pertaining to delivery of the study product.

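### The self-assessment scales do not say which site or product is being rated, and the planned two-group tests do not fit a change scale or same-person hand ratings

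*Combined protocol and SAP*

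**What the plan says.** The combined protocol and SAP lists self-assessment as Secondary endpoint 2, with a time frame of weeks 6, 12, 26 and 52. It has two instruments.

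- GAIS runs from 1 (best) to 5 (worse), anchored to the subject's starting appearance: "4 No change: Appearance essentially the same as original condition".
- The Cosmetic Improvement Scale is summarised as percentages of responses, for example "Percentage of subjects satisfied or very satisfied with the treatment". Other items cover recommending and continuing the treatment, self-esteem, and degree of improvement.

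Neither definition names a body site or a product.

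The Data Analysis Plan states one rule for all outcomes: "Treatment effects on outcomes will be compared between baseline versus HPE and HPE versus market competitor group", "with a significance level of p < 0.05". The methods are "All continuous data will be analyzed using independent 2-group t tests", chi-square tests between the two groups for categorical data, and rank-sum or Fisher exact tests as fallbacks. There is no separate rule for self-assessment.

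Under Study procedures, the same 80 subjects apply HPE to the face, decolletage and right dorsal hand, and C.E. Ferulic to the left dorsal hand.

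**The concern.** A response about the treatment, from someone using two products on several sites, cannot be assigned to either product unless the form says what is being rated. Comparing HPE with the competitor is a stated aim, and Figure 1 puts questionnaires in the competitor-hand block, so self-ratings appear meant to inform that comparison. If the forms turn out to be global, the missing ratings cannot be recovered after the visits.

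The tests are also a poor match. GAIS has the comparison with the starting condition built in, so a separate baseline group adds nothing. An analyst who follows the text literally could test week-12 GAIS against a day-0 improvement score that has no meaning, and could compare two hands of one person as though they belonged to different people.

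**Working it through.** The plan gives no effect size, SD, power or dropout for this endpoint, so there is no figure to reproduce. The main check is a comparison of sections. The arithmetic is illustrative.

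**1. What is rated.** The HPE-versus-competitor contrast needs one score per product. The item definitions supply none. Figure 1 has a separate block for the left (C.E. Ferulic) hand that includes questionnaires, so collection by site may be intended, but no section defines such an item.

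**2. When it is rated.**

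- Secondary endpoint 2: weeks 6, 12, 26 and 52, with no baseline.
- Methods: "day 0, week 6 and week 12, which will include a subject questionnaire rating subjective parameters", naming both scales.
- Table 1: questionnaires at every encounter, which includes Visit 0.
- Figure 1, HPE block: from week 6. Figure 1, left-hand block: weeks 0, 6 and 12.
- Visit 0 list: no questionnaire.

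These cannot all be right.

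**3. What a day-0 GAIS would add.** At best every subject scores 4 on day 0, with zero variance. Let d be the mean difference from 4 and s the SD at follow-up, with n = 80. The pooled variance is (s² + 0)/2, so the two-sample standard error is √(2 × s²/2 / n) = s/√n. The statistic is d/(s/√n), the same as in a one-sample test against 4, but referred to 158 degrees of freedom instead of 79. The day-0 column brings no information and doubles the apparent sample. Any day-0 answer other than 4 shifts the comparison for no interpretable reason.

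**4. Hand against hand.** Assume two-sided 5%, 80% power, 80 complete pairs, a common SD of 1 for each hand's score, and within-person correlation ρ. The normal quantiles are 1.960 and 0.842, which sum to 2.802.

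- Independent test, nominal: 2.802 × √(2/80) = 0.44 SD of the score.
- Independent test when ratings are in fact correlated: (1.960 + 0.842√(1−ρ)) × √(2/80).
- Paired test: 2.802 × √(2(1−ρ)/80).

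| ρ | Independent test, actual | Paired test |
|---|---|---|
| 0 | 0.44 | 0.44 |
| 0.3 | 0.42 | 0.37 |
| 0.5 | 0.40 | 0.31 |
| 0.7 | 0.38 | 0.24 |
| 0.9 | 0.35 | 0.14 |

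With positive correlation the independent test is conservative: it loses power but does not produce excess false positives. In units of the SD of the paired difference, the paired figure is 2.802/√80 = 0.313, or about 0.32 (0.317) with the t distribution.

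**5. Face GAIS against 4.** The one-sample detectable shift is also 2.802/√80 = 0.31 SD. An exact sign test of improved against worse, at no more than 2.5% per tail, needs at least 27 improved of 40 non-tied ratings, or 50 of 80.

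**The case against.** The strongest reply is that the forms themselves are not in the documents. The endpoint section gives anchors and summary percentages, not the questions as asked, and Figure 1's left-hand block suggests the hands may be rated separately. This stands. A reader might infer that each subject gives a single global rating and that no usable head-to-head self-ratings will exist. No section says so. What remains is that no section defines a per-hand item either.

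Second, a change scale needs no baseline, and the endpoint section and Visit 0 list omit one. Also correct: the lack of a baseline is not an error. The faults are the sections that schedule one and the test that calls for one.

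Third, a reader might infer that neither planned contrast can be carried out. That goes too far. GAIS can be tested against its own no-change value, and the hands can be compared if the forms are per hand. The Cosmetic Improvement Scale is in any case set out as descriptive percentages.

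Fourth, "Percentage of subjects reporting treatment positively or negatively affected self-esteem" might be read as pooling benefit and harm. The next item lists response categories in the same style, so these are more naturally two categories, and pooling is not stated.

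Finally, this is a secondary endpoint, and the hands are also compared on imaging under a primary one. That limits the consequence but does not settle which site or product a response describes.

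**Conclusion.** The concern holds in a limited form. For the main study through week 12, the plan does not say which site or product each self-assessment response rates, gives conflicting timing, and assigns independent two-group tests to a change scale and to ratings that are paired within person.

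The two-product problem does not extend to weeks 26 and 52, where follow-up concerns HPE on the face and decolletage, or to the 50-person substudy, for which no competitor hand is described. The timing conflict does touch the substudy, which has the same surveys including baseline.

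The 0.32 SD figure describes what 80 complete pairs could detect with a paired t test at two-sided 5% and 80% power. It does not measure the harm done by the present wording. Dropout would raise it, and many ties on a five-level scale could alter the performance of a signed-rank test. The gain over the independent test depends on a correlation the documents do not give. The change should be made; the trial's primary conclusions do not depend on it.

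**What to change.** In the main study, at weeks 6 and 12:

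- Collect GAIS and the improvement items separately for face, right hand and left hand, naming the site on the form. If per-hand forms already exist, define them in the endpoint section.
- Compare right with left hand by a Wilcoxon signed-rank test on within-person differences, in place of the independent tests.
- For face GAIS, report the full distribution and the proportion scoring 3 or better with an exact confidence interval. Test it against 4 (no change) with a one-sample signed-rank or exact sign test. This shows change from the starting condition, without a concurrent control.
- Report the remaining Cosmetic Improvement Scale items descriptively.

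Remove both scales from day 0, and bring Methods, Table 1, Figure 1, the substudy text and the endpoint time frame into agreement.

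The cost is a few more REDCap items per visit, a slightly longer questionnaire and revised analysis wording. The per-site items need to be in place before the visits, because they cannot be recovered later.
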